6.1.3. Analysis Windows for E-diary Data

Baseline window is the run-in period and includes days from the informed consent up to the day prior to the first dose of the IMP administration. The baseline average value for an efficacy variable will be calculated based on data recorded in the run-in period and prorated to 28 days using formula equation [1A] as the monthly average for analyses based on monthly windows or prorated to 7 days using formula [1B] as the weekly average or weekly value for analyses based on weekly average or weekly windows.

Note, per eligibility checks at visit 2, patients with more than 28+3 days in the run-in period will not be eligible and will not be randomized for the study. However, in case there are patients with more than 31 days of the e-diary data collected during the run-in period, all data will be used for the baseline calculation by prorating the data to 28 days for the monthly average or 7 days for the weekly average.

Postbaseline 4-week (monthly) analysis windows will be determined based on the actual dosing date as follows:

- weeks 1 to 4: from the first dose of the IMP administration to the day before IMP administration at visit 3 (week 4); for endpoints based on week 0 to 4 data
- weeks 5 to 8: from the IMP administration at visit 3 to the day before the IMP administration at visit 4 (week 8); for endpoints based on week 4 to 8 data

- weeks 9 to 12: from the IMP administration at visit 4 to the day before the EOT visit (visit 5/week 12); for endpoints based on week 8 to 12 data

Notes:

There will be no IMP administration at visit 5, and patients will return the e-diary at the visit; for patients who withdraw from the study early, the end day for the last window will be the day before EOT/early withdrawal visit; a 4-week analysis window may contain <28, 28, or >28 days.

The monthly average of an efficacy variable for each analysis window will be calculated based on data recorded in the e-diary and prorated to 28 days using formula [1A]. Missing data handling methods are provided in Section 6.1.4.

Postbaseline 1-week (weekly) analysis windows will be determined based on days in the 4-week analysis windows (derived based on the actual dosing date as described above) as follows:

- | | | |
|---|---|--|
| 
 • week 1 = day 1 to day 7 • week 2 = day 8 to day 14 • week 3 = day 15 to day 21 • week 4 = day 22 to day 28* | } | of analysis window weeks 1 to 4
(Month 1; Dose 1 to Dose 2) |
| 
 • week 5 = day 1 to day 7 • week 6 = day 8 to day 14 • week 7 = day 15 to day 21 • week 8 = day 22 to day 28* | } | of analysis window weeks 5 to 8
(Month 2; Dose 2 to Dose 3) |
| 
 • week 9 = day 1 to day 7 • week 10 = day 8 to day 14 • week 11 = day 15 to day 21 • week 12 = day 22 to day 28* | } | of analysis window weeks 9 to 12
(Month 3; Dose 3 to EOT) |

* This analysis window may contain <7, 7, or >7 days.

For patients who withdraw from the study early, the last analysis window may be <7 days.

The weekly value of an efficacy variable for each analysis window will be calculated based on data recorded in the e-diary and prorated to 7 days using formula [1B] if applicable. Missing data handling methods are provided in Section 6.1.4.

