## 6. ASSESSMENT OF EFFICACY

Data from any efficacy assessments performed after the specified time will not be collected on the CRF. However, in the event that such data are collected, these data will not be analyzed.

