6.2. Primary Efficacy Endpoint and Analysis

6.2.1. Definition

The primary efficacy endpoint of this study is the mean change from baseline (run-in period) in the monthly average number of CH attacks during the 12-week period after administration of the first dose of the IMP.

CH attacks will be derived from the e-diary data as described in Section 6.1.1. The 12-week period is the period from administration of the first dose of the IMP to the EOT/early withdrawal visit. Missing data handling methods are provided in Section 6.1.4.1.

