8.2. Duration of Exposure to Study Drug

At the visit 2, each patient will receive a 1-hour iv infusion and 3 sc injections of fremanezumab or placebo. At visits 3 and 4, patients will receive 1 sc injection of fremanezumab or placebo.

Duration of the treatment period (days) for a patient is defined as the number of days a patient is in the double-blind treatment period and calculated as date of EOT visit - first date of the IMP + 1. For patients who are lost to follow-up, the date of EOT visit is defined as the date of last IMP administration + 27. Duration of iv infusion (minutes) will be calculated for the infusion as stop date/time of infusion - start date/time of infusion. Dosing visit interval (days) is defined as the number of days between dosing visit (dose 1 and dose 2; dose 2 and dose 3) and calculated as date of next dosing - date of current dosing.

Duration of the treatment period (days), duration of iv infusion (minutes), dosing visit interval (days), the number of doses received, total number of injections received (placebo or fremanezumab), and reasons for IMP not administrated will be summarized using descriptive statistics. Summary will be presented by treatment group.

IMP administration and accountability data will be listed.

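### The diary windows have no maximum length, so after an early withdrawal without the next dose, or a late final visit, later days are counted in an earlier or longer period than the endpoint names

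*SAP*

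**What the plan says.** SAP 6.1.3 anchors the windows on doses: "Postbaseline 4-week (monthly) analysis windows will be determined based on the actual dosing date as follows". The window for the 2nd secondary endpoint is "weeks 1 to 4: from the first dose of the IMP administration to the day before IMP administration at visit 3 (week 4". Weeks 5–8 run from the visit 3 dose to the day before the visit 4 dose. The window for the 3rd secondary endpoint is "weeks 9 to 12: from the IMP administration at visit 4 to the day before the EOT visit (visit 5/week 12". For patients who withdraw early, the notes add that "the end day for the last window will be the day before EOT/early withdrawal visit; a 4-week analysis window may contain <28, 28, or >28" (counted in days).

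Within each block the first three weekly windows are fixed 7-day intervals. The fourth (weeks 4, 8 and 12) is nominally days 22–28 but may hold more than 7 days. For the primary endpoint, SAP 6.2.1 states: "The 12-week period is the period from administration of the first dose of the IMP to the EOT/early withdrawal visit".

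SAP 6.1.2 prorates each value to 28 or 7 days over the days with diary entries. SAP 6.1.4.2 and 6.1.4.3 set minimum data (10 days per month in the repeated-measures analyses, 3 per week) but no maximum.

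Two other places touch on late data. SAP 8.2 sets a substitute end date for exposure: "For patients who are lost to follow-up, the date of EOT visit is defined as the date of last IMP administration + 27". Protocol Section 6 says of efficacy assessments made after the specified time that, "in the event that such data are collected, these data will not be analyzed".

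**The concern.** The 2nd and 3rd secondary endpoints are meant to describe weeks 0–4 and weeks 8–12. Both are in the sequential testing of SAP Section 7. A window that closes only on an event can hold days outside those weeks, and proration rescales the rate without removing those days.

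The clearest case is a patient who receives dose 1, does not receive dose 2 and later has a withdrawal visit. Weeks 5–8 can start only at the visit 3 dose, so weeks 1–4 is this patient's last window. The stated rule runs it to the day before the withdrawal visit. Two things go wrong: days after week 4 enter the week 0–4 value, and month 2 has no value although the diary covered it. The same happens one block later for a patient who withdraws after dose 2 without dose 3.

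In the repeated-measures model, the diluted month and the empty month also feed the estimates for the other months. In the multiple-imputation analysis (SAP 6.2.3.1), the empty month would be imputed. Placebo data would be used for active-arm patients who left for an adverse event or lack of efficacy.

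**Working it through.** **Yardstick.** SAP 2.4 plans for a difference of 4 attacks per month with SD 8, two-sided 0.05 and at least 90% power. The formula 2 × (z₀.₉₇₅ + z₀.₉₀)² × (8/4)² gives 85 per group. The planned 86 give 90.6% power, and 258/0.86 = 300. These figures reproduce and are not in dispute; 4 attacks is the scale for what follows.

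**Compliant patients.** Window length is the number of days from the opening dose to the day before the closing event. Protocol Table 2 allows ±3 days per visit; Appendix B allows +3 only.

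| Period | Table 2 (days) | Appendix B (days) | Largest overrun |
|---|---|---|---|
| Weeks 1–4 | 25–31 | 28–31 | 3/31 = 9.7% |
| Weeks 5–8, weeks 9–12 | 22–34 | 25–31 | 6/34 = 17.6% |
| 12-week period | 81–87 | 84–87 | 3/87 = 3.4% |

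**Late final visit** (visit 4 dose on schedule). Nothing in the SAP limits these cases.

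| EOT late by | Weeks 9–12 length | Share beyond 28 days | Share of 12-week period beyond day 84 |
|---|---|---|---|
| 7 days | 35 | 7/35 = 20% | 7/91 = 7.7% |
| 14 days | 42 | 14/42 = 33% | 14/98 = 14.3% |
| 28 days | 56 | 28/56 = 50% | 28/112 = 25% |

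**Early withdrawal without dose 2** (illustrative values). Baseline is 28 attacks per 28 days. The patient has 14 attacks in days 1–28, then 1 per day on days 29–59, with the withdrawal visit on study day 60 and complete diary entries.

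- Weeks 1–4 as written: (14 + 31)/59 × 28 = 21.4, a change of 21.4 − 28 = −6.6.
- Weeks 1–4 on days 1–28: 14, a change of −14. The difference is 7.36.
- Week 4 as written covers days 22–59, which is 38 days: (3.5 + 31)/38 × 7 = 6.4, against 3.5 for days 22–28.
- Month 2 as written: no value, although days 29–56 were all recorded.
- Primary endpoint: 21.4 either way, because all 59 days lie inside the 12 weeks.

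**Arm level.** The documents give no rate of such patients. Assuming 2–5% of an arm, the raw arm mean for weeks 0–4 shifts by 7.36 × 0.02 = 0.15 to 7.36 × 0.05 = 0.37 attacks.

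**The case against.** The windows are a disclosed choice. SAP 6.1.3 ties them to actual dosing, says openly that "a 4-week analysis window may contain <28, 28, or >28 days", and treats baseline the same way: run-in data beyond 31 days are all used and prorated. Windows by dosing interval are defensible, and for patients within the visit schedule they do little harm. That stands. It does not cover the patient who has no next dose, for whom there is no dosing interval to follow.

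The worked patient is also extreme. It needs 59 days of entries after a single dose, although Protocol 4.3 asks for a final evaluation at the time of withdrawal. It also assumes a full return to the baseline rate on day 29, while Protocol 1.2.2.1 reports a mean half-life of 32.2–36.2 days in healthy subjects. The example shows how the rule works, not what is typical.

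Several stronger readings are tempting but not supported:

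- A reader might infer that all weekly windows are open-ended. Only weeks 4, 8 and 12 are; the other nine are fixed.
- A reader might infer that a missed dose stretches weeks 9–12. That window starts at the visit 4 dose, so missing it leaves no start. Only a late EOT lengthens it.
- A reader might infer that a patient who skips the visit 3 dose and continues is misallocated. The SAP does not say what closes the window in that case; it is undefined.
- A reader might infer a breach of Protocol Section 6. That section sets no specified time for diary windows, so no contradiction is shown, and it gives no working cut-off either.
- A reader might infer that patients lost to follow-up keep adding days. Formula [1A] counts only days with entries, so nothing is added once entries stop.

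**Conclusion.** The gap is real and limited. SAP 6.1.3 and 6.2.1 set no maximum for the 4-week windows, for weeks 4, 8 and 12, or for the 12-week period. For early withdrawals without the next dose, the stated rule itself puts later days in the earlier window and empties the later month. A late EOT adds days after week 12 to the week 8–12 and 12-week results.

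The confirmatory endpoints mainly affected are the 2nd and 3rd secondary endpoints, which are tested only after both primary comparisons succeed. The primary endpoint is affected only by a late EOT, and by at most 3 days when visits are on schedule. The arm-level shift of 0.15–0.37 attacks is modest against 4 and rests on an assumed prevalence and an assumed course of attacks. Since the misallocation depends on withdrawal it could differ by arm, but the documents do not show that it does. Sample size and power are unchanged.

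**What to change.** Amend SAP 6.1.3, with a cross-reference in 6.2.1, using the SAP's day numbering (first dose = day 1):

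- Keep the dose-anchored boundary when the next dose is given within its visit window.
- If the visit 3 or visit 4 dose is not given, or is given outside its visit window, end the current window on study day 28 or 56 and start the next on day 29 or 57. No day then falls in two windows.
- End weeks 9–12 and the 12-week period at the earlier of the day before EOT/early withdrawal and study day 87 (84 + 3). This also closes the window when there is no EOT visit, and it keeps a compliant 34-day window intact.
- End weeks 4, 8 and 12 with their parent window.
- Do not use later diary days for these endpoints.

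The rule needs one visit window to refer to, so Protocol Table 2 (±3 days) and Appendix B (+3 days) must be reconciled.

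In the worked example, month 1 becomes 14 and month 2 becomes 28. Days 57–59 fall in month 3, which stays missing under the 10-day minimum.

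The cost is a paragraph of SAP text and a small programming change before unblinding. The downside is that a few late diary days go unused.

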6.1.4. Handling Missing E-diary Data

This section includes missing data handling for e-diary data. For other type of data, the missing data handling methods are provided in the analysis section for the endpoint if applicable.

6.1.4.1. Primary Efficacy Endpoint

The monthly average number of CH attacks during 12-week period will be calculated based on data available and prorated to 28 days using formula [1A]. Note, patients who have < 10 days of e-diary data will be excluded from FAS and PP analysis set (Section 3).

As sensitivity analyses, the primary endpoint will be analyzed using the following methods for handling missing data :

- Multiple imputation (MI) method to impute missing weekly data
- An mixed model for repeated measures (MMRM) method to analyze the weekly data

Detail is provided in Section 6.2.3.

6.1.4.2. Analyses Based on Monthly and 12-week Window

In analyses using analysis of covariance (ANCOVA) based on 12-week window, the monthly average of an efficacy variable will be calculated based on data available and prorated to 28 days using formula [1A]; the weekly average of an efficacy variable will be calculated based on data available and prorated to 7 days using formula [1B].

Note, patients who have < 10 days of e-diary data will be excluded from the FAS and PP analysis set (Section 3).

In analyses using MMRM based on monthly analysis windows

- for patients who have ≥ 10 days of e-diary data in an analysis window, the monthly average number of CH attacks will be calculated based on data available in that analysis window and prorated to 28 days using formula [1A];
- for patients who have <10 days of e-diary data in an analysis window, the monthly average number of CH attacks for the analysis window will be considered as missing.

In analyses based on proportion based on weeks 0 to 12, the average number of CH attacks will be calculated based on data available and prorated to 28 days using formula [1A] as the monthly average. Response status will be determined based on the prorated average using formula [2].

6.1.4.3. Analyses of Mean Change from Baseline Using MMRM Method Based on 1-Week Window

For analyses of mean change from baseline using an MMRM method based on 1-week analysis window, missing data will be handled as follows:

- For patients who have ≥ 3 days of e-diary data in a week, the weekly value of an efficacy variable will be calculated based on data available and prorated to 7 days using formula [1B].
- Otherwise the weekly value of an efficacy variable will set to missing.

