### **9.3.1. Handling Withdrawals and Missing Data**

Efficacy variables from patients who do not have diary data completed for the entire study period will be imputed. For the analyses based on the proportion of responders, patients who are terminated from the study early will be considered as nonresponders. For patients who complete the study and have intermittent missing days in the e-diary, data will be prorated to 7 days. Details will be provided in the statistical analysis plan.

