6.1.2. Data Derivation

The **monthly average** of an efficacy variable will be calculated and prorated to 28 days as follows:

$$\frac{\sum \text{efficacy endpoint data during the period}}{\text{Number of Days with assessments recorded in the eDiary during the period}} \times 28 \quad [1A]$$

The **weekly average or weekly value** of an efficacy variable will be calculated and prorated to 7 days as follows:

$$\frac{\sum \text{efficacy endpoint data during the period}}{\text{Number of Days with assessments recorded in the eDiary during the period}} \times 7 \quad [1B]$$

The “efficacy endpoint data” will be “number of CH attacks”, “days with use of cluster-specific acute headache medications (triptans and ergot compounds)”, “days oxygen is used to treat CCH”, or “days with use of any headache medication”, etc.

The period will be the run-in period (including days from informed consent up to the day prior to the first dose of the IMP administration) for baseline calculation or an analysis window (eg. weeks 1 to 4, weeks 5 to 8, weeks 9 to 12, etc.) for post-baseline calculations.

The **percentage of reduction** from baseline in the monthly average number of CH attacks will be calculated as follows:

$$\frac{\text{baseline value} - \text{postbaseline value}}{\text{baseline value}} \times 100\% \quad [2]$$

where baseline value and postbaseline value are the monthly average calculated using [1A].

Note, the calculation of a proportion based on the weekly average or monthly average would yield the same results. Therefore to be consistent, all proportions will be calculated based on the monthly average number of CH attacks.

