6.3. Secondary Efficacy Endpoints and Analyses

The secondary efficacy endpoints are listed in Section 1.2. Analyses will be based on the FAS and PP analysis set.

As exploratory analyses, endpoints analyzed using an ANCOVA method will be also analyzed using MMRM method in a manner analogous to the analysis as described in Section 6.2.3.2.

6.3.1. Proportion of Patients with a $\geq 50\%$ Reduction from Baseline in the Monthly Average Number of CH Attacks During the 12-Week Period After the First Dose of the IMP

This secondary efficacy endpoint will be analyzed using Cochran-Mantel-Haenszel (CMH) test stratified by baseline preventive medication use (yes or no). Descriptive statistics (count and percent) and p-value for Row Mean Scores difference will be presented.

The 12-week period is the period from administration of the first dose of the IMP to the EOT/early withdrawal visit. CH attacks within the 12-week period will be derived from the e-diary data as described in Section 6.1.1 and prorated to 28. Missing data handling methods are provided in Section 6.1.4.2.

The proportion of reduction for a patient will be calculated using formula [2]. Responders will be those with $\geq 50\%$ reduction.

Example SAS code for CMH:

```
PROC FREQ DATA=<name>;
    TABLES BPMU*TRTP*AVALC / CMH;
    OUTPUT OUT=<name> CMH;
RUN;
```

Where TRTP denotes the planned treatment group; BPMU denotes the baseline preventive medication use (yes or no); and AVALC denotes the responses with yes for responders (with $\geq 50\%$ CH attacks reduction) and no for non-responders (with $< 50\%$ CH attacks reduction).

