16. STATISTICAL SOFTWARE

All data listings, summaries, and statistical analyses will be generated using SAS[®].

**17. CHANGES TO ANALYSES SPECIFIED IN THE STUDY
PROTOCOL**

None.

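### The SAP scores early withdrawals on their prorated partial diary for the ≥50% responder endpoint; the protocol makes them non-responders, and the change is undeclared

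*SAP*

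**What the plan says.** Protocol 9.3.1 gives the rule for withdrawals: "For the analyses based on the proportion of responders, patients who are terminated from the study early will be considered as nonresponders". The next sentence covers proration and limits it to completers: "For patients who complete the study and have intermittent missing days in the e-diary, data will be prorated to 7 days".

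SAP 6.1.4.2 handles proportions over weeks 0 to 12 differently: "the average number of CH attacks will be calculated based on data available and prorated to 28 days using formula [1A] as the monthly average". It then says: "Response status will be determined based on the prorated average using formula [2]". Formula [1A] in SAP 6.1.2 divides by the "Number of Days with assessments recorded in the eDiary during the period", not by 84. SAP 6.3.1, which covers the first secondary endpoint, refers to 6.1.4.2 for missing data and defines the window: "The 12-week period is the period from administration of the first dose of the IMP to the EOT/early withdrawal visit". Its responder definition has no completion requirement: "Responders will be those with $\geq 50\%$ reduction".

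The only floor is in SAP 3.3 and 6.1.4.2. Patients with fewer than 10 post-baseline diary days are left out of the full analysis set (FAS); they are not counted as failures. Section 17 of the SAP, headed "17. CHANGES TO ANALYSES SPECIFIED IN THE STUDY" protocol, has the single entry None. The SAP Introduction says that the SAP is meant to agree with the protocol, above all on the primary and secondary endpoints, and that the SAP governs where they differ.

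**The concern.** The two documents classify the same patient in opposite ways on an alpha-controlled endpoint, and the version that governs is the undeclared one. A patient who stops for an adverse event after a short quiet spell becomes a 12-week responder, although nothing is known about the remaining weeks. Short records also cross the 50% line by chance more often than full ones, so the endpoint no longer means the same thing for leavers and completers.

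The responder endpoint is the first test after the primary in the SAP Section 7 sequence, so its result decides whether any later secondary test can be interpreted. The same derivation feeds the ≥75%, 100% and cumulative responder analyses (SAP 6.4.1 and 6.4.7). In 6.4.7 only a missing value scores as non-response, and a prorated value is not missing.

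The SAP is also inconsistent with itself. In the multiple-imputation analysis of the primary endpoint (6.2.3.1), active-arm patients who leave for adverse events or lack of efficacy have their missing months imputed as if they were on placebo. The responder analysis can credit the same patients with success.

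**Working it through.** **Plan's own figures.** The documents give no sample-size figure for the responder endpoint. The primary-endpoint figure reproduces: n per arm = 2 × (1.960 + 1.282)² × 8² / 4² = 84.1, rounded up to 85. The exact t-test gives 89.99% power at 85 and 90.3% at 86, so 86 is right. 258 / 0.86 = 300 randomized. None of this changes under either rule. At 14% discontinuation, about 14 patients per arm (42 of 300) are affected, less any excluded for fewer than 10 diary days.

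**Classification under the SAP formulas.** Monthly average = attacks recorded / diary days × 28 ([1A]). Reduction = (baseline − post-baseline) / baseline ([2]). Take a patient who withdraws with 10 diary days, which is 10/84 = 11.9% of the period:

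| Baseline per 28 days | Attacks in 10 days | Prorated | Reduction | SAP | Protocol |
|---|---|---|---|---|---|
| 10 (eligibility minimum) | 1 | 2.8 | 72% | responder | non-responder |
| 20 | 3 | 8.4 | 58% | responder | non-responder |
| 30 | 5 | 14.0 | 53% | responder | non-responder |

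**Chance response on short records.** This was simulated with no treatment effect and no true change: a 28-day baseline with at least 10 attacks, a mean of 15 to 28 attacks per 28 days, and weekly negative binomial counts with dispersion (size) parameter 1 to 4. The attack means and the dispersion are assumptions; the documents give neither. Probability of an apparent reduction of at least 50%:

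| Diary days | Overdispersed | Poisson |
|---|---|---|
| 10 | 16-40% | 6-14% |
| 28 | 7-29% | 1-5% |
| 42 | 4-23% | 0-2% |
| 56 | 3-21% | 0-2% |
| 84 | 2-16% | under 1% |

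**Effect on the arm difference.** Per 100 patients, let w be the number of early leavers and p the share of them who look like responders on partial data. The SAP rule adds w × p to each arm's rate, so it shifts the difference by w(active) × p(active) − w(placebo) × p(placebo). All rates below are assumed, with completer response of 40% on active and 30% on placebo.

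- Dropout 20% active, 8% placebo. Protocol rule: 0.40 × 80 − 0.30 × 92 = 32.0 − 27.6 = 4.4 points. SAP rule with p = 0.5 in both arms: (32 + 10) − (27.6 + 4) = 10.4 points. With p equal to the no-effect 10-day range of 0.16 to 0.40: 4.4 + 12p = 6.3 to 9.2 points.
- Dropout reversed, 8% active and 20% placebo, p = 0.5. Protocol rule: 36.8 − 24.0 = 12.8. SAP rule: (36.8 + 4) − (24 + 10) = 6.8.
- Dropout 14% in each arm, p = 0.5. The difference is unchanged; both rates rise by 14 × 0.5 = 7 points.
- Dropout 14% in each arm, p = 0.6 in one arm and 0 in the other. The difference moves by 14 × 0.6 = 8.4 points either way.

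**The case against.** The conflict in the text is not disputed. The case on the other side concerns size and authority.

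- **Size.** The 10.4-point figure assumes that half of early leavers look like responders, which is above both completer rates and above the no-effect range at 10 days. No document supports 20% against 8% dropout. Ten days is the extreme, and the chance-response rate falls as follow-up lengthens. This stands: the figure is one illustrative point at the high end.
- **Direction.** The SAP rule can be conservative, as the reversed example shows. A patient leaving for lack of efficacy will usually have many attacks and prorate to non-response. Both points stand. They limit any claim that the rule favours the drug, but not the claim that it pulls towards the arm with more early leavers when partial response is similar.
- **Safeguards.** The responder analysis is repeated on the per-protocol set, which requires completion. That removes early leavers rather than scoring them as failures, so it does not restore the protocol rule. The sensitivity analyses in SAP 6.2.3 cover only the primary endpoint.
- **Authority.** Protocol 9 and 9.3.1 leave changes and details to the SAP, and 9.16 lets deviations be described there or in the study report. But 9.16 also requires the deviation and its reason to be described, and Section 17 declares none.
- **Reach.** The primary endpoint is untouched, the responder test runs only if both primary comparisons succeed, and the 75%, 100% and cumulative analyses are exploratory. True, but the responder test is still confirmatory.

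**Conclusion.** The concern holds and must be fixed. On the first secondary endpoint the SAP reverses a rule stated in the protocol, takes precedence over it, and records no change. Ten diary days is the effective minimum for being called a 12-week responder in the FAS.

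That conclusion rests on the text alone. The numerical effect rests on assumptions. About 14% of patients are exposed to the conflict. The responder difference may move by several points in either direction, depending on dropout and on attack counts before withdrawal in each arm. It does not move if both are equal, although both reported rates then rise.

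**What to change.** In SAP 6.1.4.2 and 6.3.1, and so in 6.4.1 and 6.4.7, set response to No for every FAS patient who terminated the study early, as Protocol 9.3.1 states. Prorate only for patients who completed the study. Keep the prorated classification of all FAS patients as a sensitivity analysis. State explicitly how withdrawals with fewer than 10 diary days are treated, since the FAS definition now removes them instead of scoring them.

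If the sponsor prefers proration as the main rule, Section 17 must declare and justify the change, and the non-responder rule should become a planned sensitivity analysis.

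The cost is one sentence in the SAP and one completion flag in the analysis dataset. No sample size changes. Reported responder rates fall by the share of patients who would otherwise have been credited on partial data: 7 points per arm if half of a 14% dropout qualified, less if fewer did.
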